4.2 Exclusion Criteria

The presence of any of the following will exclude a patient from study enrollment:

- History of severe hypersensitivity reaction to any monoclonal antibody.
- Patients are excluded if they have known HIV/AIDS.
- Major surgery (eg, cystectomy) less than 28 days prior to the first dose of study drug.
- Any condition requiring systemic treatment with either corticosteroids ($> 10 \text{ mg}$ daily prednisone equivalent) or other immunosuppressive medications within 7 days prior to the first dose of study drug. Inhaled steroids and adrenal replacement steroid doses $> 10 \text{ mg}$ daily prednisone equivalent are permitted in the absence of active autoimmune disease.
- Known medical condition (eg, a condition associated with diarrhea or acute diverticulitis) that, in the investigator's opinion, would increase the risk associated with study participation or study drug administration or interfere with the interpretation of safety results.
- Pregnant women are excluded from this study because animal studies have demonstrated that PD-1/PD-L1 inhibitors can cause fetal harm when administered to pregnant women. Breastfeeding women are excluded from this study because PD-1/PD-L1 inhibitors may be excreted in human milk and the potential for serious adverse reactions in nursing infants.⁴³

4.3 Inclusion of Women and Minorities

Men, women and members of all races and ethnic groups are eligible for this trial.

6.0 TREATMENT PLAN

6.1 Checkpoint Inhibitor Treatment Regimen Overview

Treatment will be administered on an outpatient basis and administered as the following:

- Pembrolizumab 200 mg IV over 30 minutes every 3 weeks
- Pembrolizumab 400 mg IV over 30 minutes every 6 weeks (Decision on pembrolizumab dose will be based on provider discretion).
- Atezolizumab 1200 mg IV over 60 minutes every 3 weeks. (if first dose is tolerated, all subsequent infusions may be delivered over 30 minutes)
- Durvalumab 10 mg/kg IV over 60 minutes every 2 weeks.
- Nivolumab 480mg IV over 30 minutes every 4 weeks
- Avelumab 800 mg IV over 60 minutes every 2 weeks

*Please refer to Section 9.0 for further pharmaceutical details.

6.2 Checkpoint Inhibitor Reactions: follow Institutional guidelines. In the absence of any such guidelines, or per provider discretion, apply the following:

For Grade 1 symptoms: Mild reaction; itching, rash, hives, fever, rigors): Stop the infusion, notify provider and study nurse. Initiate normal saline infusion at 500ml/hr, titrate up to maintain systolic BP >100. Administer diphenhydramine 50mg IV. Remain at bedside and monitor subject until recovery from symptoms.

The following prophylactic pre-medications are recommended for future infusions: diphenhydramine 50 mg (or equivalent) and/or paracetamol 325 to 1000 mg (acetaminophen) at least 30 minutes before additional CPI administrations.

For Grade 2 symptoms: Moderate reaction such as SOB, chest tightness, back pain, which requires therapy or infusion interruption but responds promptly to symptomatic treatment Follow above for Grade 1 and add oxygen at 2L via nasal cannula and titrate to

keep O₂ saturation > 92% and give hydrocortisone 100mg IVP once; remain at bedside and monitor subject until resolution of symptoms. If symptoms progress, do not re-dose medications already given, move on to treatment for severe / Grade 3 reactions. If the infusion is interrupted, then restart the infusion at 50% of the original infusion rate when symptoms resolve; if no further complications ensue after 30 minutes, the rate may be increased to 100% of the original infusion rate.

Monitor subject closely. If symptoms recur, then no further CPI will be given. Diphenhydramine 50 mg IV and remain at bedside and monitor the subject until resolution of symptoms. The amount of study drug infused must be recorded on the electronic case report form (eCRF). The following prophylactic pre-medications are recommended for future infusions: diphenhydramine 50 mg (or equivalent) and/or paracetamol 325 to 1000 mg (acetaminophen) should be administered at least 30 minutes before additional CPI administrations. If necessary, corticosteroids (recommended dose: up to 25 mg of IV hydrocortisone or equivalent) may be used.

For Grade 3 or Grade 4 symptoms: (Severe reaction, anaphylaxis, bronchospasm, stridor, wheezing, respiratory distress, angioedema, systolic BP < 80mm Hg, or LOC. Grade 3: prolonged [ie, not rapidly responsive to symptomatic medication and/or brief interruption of infusion] recurrence of symptoms following initial improvement; hospitalization indicated for other clinical sequelae [eg, renal impairment, pulmonary infiltrates]). Grade 4: (life threatening; pressor or ventilatory support indicated): Immediately discontinue infusion of nivolumab. Follow guidelines for Grades 1 and 2 and add the following: Activate emergency response team as appropriate. Administer medications from Grade 1 and 2 reaction guidelines if not yet given and add Epinephrine 0.2 to 1 mg of a 1:1,000 solution for subcutaneous administration or 0.1 to 0.25 mg of a 1:10,000 solution. Subject should be monitored until the investigator is comfortable that the symptoms will not recur. CPI will be permanently discontinued.

In the case of late-occurring hypersensitivity symptoms (eg, appearance of a localized or generalized pruritis within 1 week after treatment), symptomatic treatment may be given (eg, oral antihistamine, or corticosteroids).

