7.1 Dose Delay Criteria

CPI administration should be withheld for the following:

1. Any grade 3 drug-related AE
2. Any drug-related AE requiring the initiation of prednisone >10 mg per day (or equivalent steroid dose).
3. Any AE, laboratory abnormality, or intercurrent illness which, in the judgment of the investigator, warrants delaying the dose of study medication.

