7.2 Criteria to Resume Treatment

Subjects may resume treatment when the following criteria are met

1. Subjects may resume treatment when any drug-related laboratory or clinically AE revert to grade 1 or less.
2. Any AE that in the judgment of the investigator has sufficiently resolved.
3. Prednisone < 10mg per day (or equivalent steroid dose).

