7.3 Discontinuation Criteria

Treatment should be permanently discontinued for the following:

1. Any grade 4 drug-related AE warrants permanent discontinuation, unless it is a reversible endocrinopathy.
2. Any adverse event, laboratory abnormality, or intercurrent illness which, in the judgment of the Investigator, presents a substantial clinical risk to the subject with continued CPI dosing

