9.0 PHARMACEUTICAL INFORMATION

9.1 Pembrolizumab Product Information

Product description and dosage form	Potency	Primary Packaging (volume)/Label type	Appearance	Storage condition (per label)
Pembrolizumab Solution for Injection	100 mg/Vial (25 mg/mL)	4 mL type 1 flint glass vials	Clear to opalescent, colorless to pale yellow liquid. May contain particles	Stores at 2 to 8 degrees Celsius (36 to 46 degrees Fahrenheit) and protected from light and freezing.

Please refer to FDA package insert for further details.

(https://www.accessdata.fda.gov/drugsatfda_docs/label/2016/125514s012lbl.pdf)

Pembrolizumab will be given every three weeks at a dose of 200 mg to be administered as a 30 minute IV infusion. Pembrolizumab can also be given every six weeks at a dose of 400 mg to be administered as a 30 minute IV infusion. Decision on pembrolizumab dose will be based on provider discretion.

Subjects may be dosed every 21 days (or 42 days for 400mg dose) +/- 3 days from the previous dose of drug. There are no premedications recommended for pembrolizumab on the first cycle. Subjects should be carefully monitored for infusion reactions during pembrolizumab administration. If an acute infusion reaction is noted, subjects should be managed according to Section 6.1.

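### Where Section 6.2 applies, a grade 3 infusion reaction ends CPI permanently, while Sections 7.1–7.3 permit a restart; no precedence is stated

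*Combined protocol and SAP*

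**What the plan says.** **Reaction rules.** Section 6.2 sends sites first to their institutional guidelines. Its own rules apply where there are none, or where the provider chooses to use them. Grades 3 and 4 share one instruction, which opens "For Grade 3 or Grade 4 symptoms: (Severe reaction, anaphylaxis, bronchospasm, stridor, wheezing" and closes "Subject should be monitored until the investigator is comfortable that the symptoms will not recur. CPI will be permanently discontinued".

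**Dose delay and discontinuation rules.** Section 7.1 lists among its reasons to withhold CPI: "Any grade 3 drug-related AE". Section 7.2 then provides: "Subjects may resume treatment when any drug-related laboratory or clinically AE revert to grade 1 or less". Section 7.3 item 1 reads: "Any grade 4 drug-related AE warrants permanent discontinuation, unless it is a reversible endocrinopathy". Item 2 of the same section adds permanent discontinuation for any event that the investigator considers too risky for dosing to continue.

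**Study status.** Section 6.4 item 3 removes patients for unacceptable toxicity and refers only to Section 7.3. Item 5 lets the investigator remove a patient whose condition no longer allows treatment.

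**Restarting.** Under Section 3.3, patients who progress by RECIST in the intermittent phase should restart CPI. Section 2.2 makes response to re-initiation a secondary objective.

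**The concern.** One clinical event falls under two sets of rules with different consequences. A site that follows Section 6.2 stops CPI for good after a grade 3 infusion reaction. A site that follows Section 7 may hold CPI and give it again once the event has settled. Whether a patient is re-exposed after a severe reaction is a safety decision, and it should not depend on which section the site reads.

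The design makes the question practical, because re-exposure after a break is part of the strategy under test. The answer also determines who can contribute to the secondary objective on re-initiation. Study status is unclear as well: a patient stopped under Section 6.2 at grade 3 meets no mandatory toxicity criterion for removal, because Section 6.4 item 3 looks only to Section 7.3.

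**Working it through.** The plan states no figure on this point and no arithmetic applies. The check is to trace one event through each section.

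**Step 1: is an infusion reaction covered by Section 7?** Section 8.1 calls an event related when there is a reasonable causal link with giving the study drug. A reaction to a CPI infusion fits that definition. Sections 7.1–7.3 make no exception for infusion reactions.

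**Step 2: grade 3 and grade 4 reactions, section by section.**

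| Section | Grade 3 infusion reaction | Grade 4 infusion reaction |
|---|---|---|
| 6.2 (where its rules apply) | Permanent discontinuation, mandatory | Permanent discontinuation, mandatory |
| 7.1 | CPI withheld | Governed by 7.3 |
| 7.2 | May resume at grade 1 or below | Governed by 7.3 |
| 7.3 item 1 | Not triggered | Permanent discontinuation, mandatory |
| 7.3 item 2 | Discontinuation possible, by judgment | Already mandatory under item 1 |
| 6.4 item 3 | Removal only if 7.3 is met, so only by judgment | Removal through 7.3 |

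At grade 4, Sections 6.2 and 7.3 agree. The disagreement is confined to grade 3.

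**Step 3: does the text settle it?** Section 7 does not refer to Section 6.2, Section 6.2 does not refer to Section 7, and no order of precedence is given. Section 7.0 cites a guideline on immune-related events, but Sections 7.1 and 7.2 are worded for drug-related events in general. Institutional guidelines, which come first under Section 6.2, may supply a third rule whose standing against Section 7 is also unstated.

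**Step 4: which patients and which results can be touched?** Section 4.1 requires at least 20 weeks of prior CPI, and Section 4.2 excludes anyone with a past severe hypersensitivity reaction to a monoclonal antibody. The conflict therefore concerns new reactions on study, in patients who have largely tolerated CPI already. In the intermittent phase no CPI is given until progression (Section 3.3). A reaction at restart thus comes after the progression that already counts for the 24-week monitoring or the 36-week endpoint. The stopping boundaries in Table 1 and the exact confidence interval in Section 14.3 do not depend on the rule. What remains is dosing of patients still on CPI, and re-initiation after progression.

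**Step 5: related wording.**
- After a grade 2 reaction the text says "If symptoms recur, then no further CPI will be given", without stating whether this means that infusion or every later one. Pre-medication for later infusions is recommended shortly afterwards. Section 6.2 also lists symptoms that return after first improving under grade 3, so the boundary with the grade 3 rule is not sharp.
- The grade 3 and 4 instruction says "Immediately discontinue infusion of nivolumab", although Section 6.1 lists five agents.
- Section 9.1 says "If an acute infusion reaction is noted, subjects should be managed according to Section 6.1", and Sections 9.2–9.5 send sites to the same place. Section 6.1 holds the dosing list; the reaction rules are in 6.2.

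**The case against.** The strongest reply is that a site can comply with every section at once. Section 7.2 permits resumption without requiring it, and Section 7.3 item 2 allows permanent discontinuation by judgment. A site may therefore hold under 7.1, stop under 6.2 and breach nothing. Section 6.2 is also the more specific text, and Section 7.0 leans on a guideline for immune-related events, so it is natural to let 6.2 govern reactions. Section 6.4 item 5 offers a route to removal that does not depend on 7.3.

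Much of this stands, and it rules out a reading that a reader might be tempted by: that the sections give opposite orders and Section 7 tells sites to re-dose. It does not. The reply nevertheless leaves the gap open. A site that relies on Section 7 and resumes is also following the protocol as written, because no text gives the specific rule priority or limits Section 7 to immune-related events. The deference to institutional guidelines shows that the 6.2 stop is conditional, but it adds a further possible rule and settles nothing.

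On grade 2, a reader might infer the same conflict. The sentence directly follows the steps for restarting the interrupted infusion, so it most naturally refers to that infusion, with the pre-medication advice meant for later ones. It needs clarifying but is not a second contradiction. The nivolumab wording and the Section 6.1 references are likewise editorial slips.

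**Conclusion.** The inconsistency is real and sits in the current text. For a grade 3 infusion reaction, Section 6.2 (where its rules apply) mandates a permanent stop, Sections 7.1–7.2 permit a restart, and nothing ranks them. Study status after a stop under 6.2 is left to judgment. The case for correcting it rests on patient safety at on-study dosing and at re-initiation after progression, not on statistics.

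Probably few patients are affected. This is inferred from the eligibility criteria, since the documents give no infusion-reaction rate. A reader might apply an assumed percentage to the enrolment ceiling of 75, or count one affected patient as 1/20 = 5% of the intermittent arm. The documents support neither. Entrants have already had at least 20 weeks of CPI, and patients in the intermittent phase receive none until they progress. The primary endpoint, the stopping boundaries and the confidence interval are unaffected.

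The conclusion assumes that an infusion reaction counts as a drug-related adverse event, as the Section 8.1 definition implies. It takes no view on which clinical rule is right.

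**What to change.** The sponsor should reconcile Sections 6.2, 6.4 and 7.1–7.3 so that one stated rule governs grade 3 infusion reactions. The text should say how that rule ranks against institutional guidelines, and whether a patient stopped under it stays on study. Which rule applies is the sponsor's decision.

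Editorial points for the same amendment:
- State whether the grade 2 recurrence sentence means that infusion or all later ones, and align it with the pre-medication advice.
- Reconcile the nivolumab-only stop instruction with the five permitted agents.
- Correct the references to Section 6.1 in Sections 9.1–9.5, since the reaction rules are in 6.2.

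The cost is wording in Sections 6, 7 and 9 of one amendment. It adds no patients, procedures or analyses.

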6.3 General Concomitant Medications and Supportive Care Guidelines

The following medications are prohibited during the study:

- Any concurrent antineoplastic therapy (ie, chemotherapy, hormonal therapy, immunotherapy, extensive radiation therapy, or standard or investigational agents for treatment of cancer).

Palliative (limited-field) radiation therapy is permitted, if all of the following criteria are met:

- The lesion being considered for palliative radiation is not a target lesion.

6.4 Criteria for Removal from Study

Patients will be treated per protocol until:

1. RECIST-PD (treating MD may continue CPI). Study PI must be informed via email (or Site Communication Form") that subject is continuing based on clinical benefit. These patients will continue per normal imaging schedule (every 12 weeks).
2. Patients on CPI treatment who develop a RECIST-PD (PD1) can continue CPI treatment if there is clinical benefit. If on subsequent imaging they continue to have RECIST-PD (PD2), they will be removed from trial.
3. Unacceptable toxicity (see Section 7.3)
4. Withdrawal of consent
5. General or specific changes in the patients' condition that render the patient unacceptable for further treatment in the judgment of the investigator.
6. Any patient who on consecutive imaging (i.e., for 24 weeks) has SD while on therapy and does not achieve > 10% tumor burden reduction will be removed from the trial.

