2.2 Secondary Objective(s)

[figure not shown]
- To determine the clinical outcome (TFI, ORR, PFS, OS) in advanced urothelial carcinoma with intermittent CPI therapy.
- To assess response to re-initiation of CPI therapy

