3.3 Expected Duration of Treatment and Subject Participation

Each study cycle consists of 14-28 days, depending on which CPI is chosen. CPI of choice will be administered on day 1.

All patients who do not meet criteria for the CPI intermittent phase of the study will be treated until unacceptable toxicity or RECIST-defined PD. Patients with RECIST-defined PD may continue CPI therapy at the discretion of the treating MD. These patients will continue with normal imaging every 12 weeks. In cases where a patient is continued on therapy after PD and develops subsequent PD ($\geq 20\%$ increase in sum of target lesions compared to the initial PD tumor measurements, the patient will come off study).

Patients who meet criteria for the intermittent phase (i.e., have $\geq 10\%$ tumor burden reduction) will not receive CPI therapy. Imaging will continue per protocol (every 12 weeks from the initial date they stopped CPI therapy). Patients who have RECIST defined PD on the intermittent phase should reinitiate CPI therapy. Patients who have a subsequent decrease in tumor burden $\geq 10\%$ can then restart CPI therapy as per protocol. (refer to schema in Section 3.1).

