11. Bone imaging: Bone scan to be performed if clinically indicated.
12. Biopsy is recommended at any time during cycle 1 (for PR and SD patients) and within 3 weeks of any other time period at which a PD or PR is achieved in any patient (unless not feasible or unsafe per investigator discretion. Archival tissue up to 6 months prior to enrollment is acceptable in lieu of a cycle 1 biopsy
13. OFF treatment Patients will be seen every 12 weeks. The 6-week interim visit between scans will be done if clinically indicated. Labs during the 6-week interim visit should be as clinically indicated.
14. End of treatment: End of treatment visit is defined as the visit during which the patient will be removed from the study (even if not receiving drug at that visit).
15. Post- study follow up Patients will continue to be followed for at least 30 days after the last dose of CPI therapy or until new anti-cancer treatment is initiated, whichever comes first. Phone follow-up is sufficient.

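### Section 6.4 does not separate stopping CPI from leaving the study for off-therapy patients: item 1 conflicts with 3.3, and item 3 can cost a responder's week-36 outcome

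*Combined protocol and SAP*

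**What the plan says.** **Removal.** The heading is "6.4 Criteria for Removal from Study", but the sentence that introduces the list is "Patients will be treated per protocol until". Item 1 is "RECIST-PD (treating MD may continue CPI", and of patients kept on CPI it adds "These patients will continue per normal imaging schedule (every 12 weeks". Item 3 is "Unacceptable toxicity (see Section 7.3". Neither item is limited to patients receiving drug, whereas items 2 and 6 are. Section 7.3, to which item 3 points, lists reasons to stop treatment permanently. Item 5 covers changes in condition, by investigator judgement.

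**PD while off therapy.** Section 3.3 says "Patients who have RECIST defined PD on the intermittent phase should reinitiate CPI therapy". The synopsis and 3.1 agree, and the study calendar has a visit column that includes patients restarting CPI. Section 2.2 lists the objective "To assess response to re-initiation of CPI therapy".

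**End of treatment and follow-up.** Footnote 14 of the calendar defines the end-of-treatment visit as the one at which "the patient will be removed from the study (even if not receiving drug at that visit". At and after that visit the calendar requires tumor imaging only if clinically indicated. Section 6.5 and footnote 15 guarantee follow-up for 30 days after the last dose, or until new anti-cancer treatment if that is earlier.

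**Endpoints.** Section 14.3 makes sustained response at 36 weeks after suspension the primary endpoint, with 20 patients and an exact 95% CI half-width of at most 0.23. Section 14.2 makes progression at 24 weeks the safety endpoint. The only counting rule, also in 14.2, treats progression, death from disease or loss to follow-up before 12 weeks as failure.

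**The concern.** The list in 6.4 appears to be written for patients on CPI, yet the patients who carry the primary endpoint are off it. For them, the end of treatment and the end of the study are different events, and the protocol treats them as one.

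For PD, item 1 offers one exception, that the physician may continue CPI. That does not fit a patient who is not receiving CPI. A site that follows 6.4 could close out a patient whom 3.3 keeps on study, and that patient's response to restarting would not be recorded.

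For toxicity, a suspended patient has no treatment to stop, so under this heading the only effect left is removal. The patient may still be in response. Scheduled scans would end, and Section 14 does not say how the patient then counts at week 24 or week 36.

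**Working it through.** **1. Item 1 against the rest of the protocol.**

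| Place | Patient with PD while off CPI |
|---|---|
| 6.4 item 1 | On a list of removal criteria; the only exception is continuing CPI |
| 6.4 item 2 | Not covered (limited to patients on CPI) |
| Synopsis, 3.1, 3.3 | Restarts CPI |
| Calendar | Has on-study visits for restarting patients |

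These cannot all be followed as written. What is at stake is the re-initiation objective. The primary outcome is not affected: a patient with PD before week 36 has not sustained a response, so the result is known at the time of PD.

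*How many patients could restart by week 36.* Section 14.2 uses 0.40 in two ways, as the prior mean for PD at 24 weeks and as the progression expected within one year. Assuming a constant hazard and 20 patients:
- 0.40 at 24 weeks: 1 − 0.6^(36/24) = 0.535, and 0.535 × 20 = 10.7.
- 0.40 at 52 weeks: 1 − 0.6^(36/52) = 0.298, and 0.298 × 20 = 6.0.

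So about 6 to 11 patients would meet the conflicting text by week 36. Patients who progress later would add to this.

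**2. Item 3 for a suspended responder.** Take a patient who meets 7.3 at week 14 of suspension.
- Item 3 lists the event and has no off-therapy exemption.
- Footnote 14 says removal applies even if no drug is being given.
- Week 14 is 14 × 7 = 98 days after suspension, so the 30-day minimum in 6.5 has already passed.
- After removal no scan is scheduled. Counting 12-weekly from suspension, as in 3.3, the scans at weeks 24 and 36 are lost.
- The rule in 14.2 does not name removal for toxicity.

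**3. Size for the primary estimate.** The plan's own figure comes first. The exact (Clopper-Pearson) limits are the 0.025 quantile of Beta(x, n − x + 1) and the 0.975 quantile of Beta(x + 1, n − x). At n = 20 the interval is widest at x = 10: 0.272 to 0.728, half-width (0.728 − 0.272)/2 = 0.228. The stated 0.23 is reproduced.

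The documents give no rate of late toxicity off therapy. I assume 1 to 4 such removals among 20 patients and, for illustration, 10 successes among the others.

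| Removed (assumed) | Maximum half-width if excluded | Counted as failures | Excluded | Counted as successes |
|---|---|---|---|---|
| 1 | 0.233 (n = 19) | 10/20 = 0.50 | 10/19 = 0.526 | 11/20 = 0.55 |
| 2 | 0.240 (n = 18) | 10/20 = 0.50 | 10/18 = 0.556 | 12/20 = 0.60 |
| 3 | 0.246 (n = 17) | 10/20 = 0.50 | 10/17 = 0.588 | 13/20 = 0.65 |
| 4 | 0.253 (n = 16) | 10/20 = 0.50 | 10/16 = 0.625 | 14/20 = 0.70 |

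Each patient moves the estimate by 1/20 = 5 percentage points between the two extremes. One exclusion gives 0.233, which still rounds to 0.23; from two on the limit is passed after rounding as well.

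**The case against.** The strongest case is that 6.4 is a general list and need not override specific text. Its opening sentence concerns treatment. Item 1 foresees continued CPI with continued imaging, and only items 2 and 6 state removal outright. PD off therapy is dealt with in the same way in the synopsis, 3.1, 3.3 and the calendar, and restarting is a stated objective. Most sites would probably follow 3.3.

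This stands against a stronger reading, that every patient with off-therapy PD leaves and the re-initiation sample is empty. A reader might infer that from the heading and item 1, but it is the literal worst case and not an expected loss. It does not remove the conflict, because the heading and footnote 14 both speak of leaving the study.

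On toxicity, 3.3 has no rule for off-therapy patients, so item 3 contradicts nothing there; it is a gap. Section 7.3 concerns stopping treatment, and a bar on future CPI need not end follow-up. Footnote 14 fixes the timing of a visit and adds no removal criterion. All of this is fair. But the documents nowhere say that an off-therapy patient who meets item 3 stays on the 12-weekly scans, and read together, 6.4, 6.5 and footnote 14 allow the opposite.

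Finally, the spread in the table rests on assumed counts and also reflects the missing counting rule in Section 14. Rewording 6.4 does not settle how other dropouts count.

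**Conclusion.** The point holds in two parts of different kinds.

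(a) Item 1 of 6.4 and the synopsis, 3.1, 3.3 and calendar are inconsistent for PD that occurs off therapy. Taken literally, item 1 costs data on response to re-initiation, with some 6 to 11 of 20 patients meeting the conflicting text by week 36 under a constant hazard. It would be wrong to infer that PD also costs the week-36 outcome; those patients are already failures.

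(b) Item 3, with footnote 14 and 6.5, leaves room to remove a suspended patient still in response before week 24 or week 36 status is known. Each such patient is worth 5 percentage points of the primary estimate. With 1 to 4 excluded, the maximum half-width is 0.233 to 0.253 against the stated 0.23. The counts are assumed, since the documents support no particular rate.

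No stated statistical figure is wrong. The change is worth making before enrollment is complete because the arm is small and the scans are already scheduled.

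**What to change.** - Reconcile 6.4 item 1 with 3.3 for PD that occurs off therapy. Which clinical rule applies is for the investigators to settle.
- In 6.4 and footnote 14, separate the end of study treatment from the end of study follow-up.
- State that intermittent-arm patients who meet item 3 or item 5 while off therapy and without PD continue to have their scheduled 12-weekly scan results recorded to PD or week 36, unless consent is withdrawn.
- Leave the second-progression rule in item 2 as it is, and keep recording scans after re-initiation for patients who restart CPI. Stopping at PD for them would defeat the re-initiation objective.

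The cost is a change of wording and some data entry. A patient removed at week 14 needs two more scan results (weeks 24 and 36); one removed before week 12 needs three. No scan is added to the existing schedule.
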